To support this interval, this study aims to produce data of the response in healthy volunteers to our ChAdOx-1 HBV vaccine following the use of the AZD1222 vaccine. T cell responses (the critical immunological factor in chronic HBV infection) will be compared in participants who have received either a prior two-dose series of AZD1222 with those who have received at least two prior doses of either the Pfizer mRNA COVID 19 vaccine (Comirnaty) or the Moderna COVID-19 vaccine (Spikevax). Due to the recommendation to use the AZD1222 in those over the age of 40 years, we will confine our study to 40-60 years of age and keep the interval from the latest COVID-19 vaccine to a narrow window of 10-18 weeks. No interference on HBV -focused T cell responses is expected from either the Pfizer vaccine or the Moderna vaccine, so the interval from the latest COVID-19 vaccine will be between 6 to 30 weeks

2

STUDY OBJECTIVES AND ENDPOINTS

Objectives	Endpoints
Primary	Primary
Determine the safety and tolerability of different doses of a single vaccination of ChAdOx1-HBV in healthy participants and in participants with CHB infection and virally suppressed with oral antiviral medication.	Incidence of safety and reactogenicity events: 
 • Adverse events and/or adverse events leading to study discontinuation • Serious adverse events • Grade ≥ 3 local and systemic reactions
Secondary	Secondary

 • Determine the immunogenicity of ChAdOx1-HBV in (A) healthy participants and in (B) participants with CHB, virally suppressed with oral antiviral medication 
Determine the effect of ChAdOx1-HBV on the level of HBsAg in participants with CHB infection, virally suppressed with oral antiviral medication
	
 • A multi-parameter index made of CD4+ magnitude, CD4+ avidity, and CD8+ magnitude • Mean reduction in HbsAg titre at Day 84 and Day 168 post-vaccination (last visit) • Proportion of CHB participants with HbeAg and HbsAg loss • Proportion of CHB participants with HbeAg and HbsAg seroconversion • Reduction of hepatitis B DNA levels • Total T cell response to the antigens encoded by ChAdOx1-HBV as measured in a peptide-stimulated ELISpot assay
Exploratory	Exploratory

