3.3 Benefit Risk Assessment

There are potential known and unknown risks associated with vaccination. With any vaccine, including those that are licensed, there is a rare risk of anaphylaxis which can be fatal. All participants will be observed in the clinic for at least 30 minutes post-vaccination.

Intramuscular injection of vaccines frequently causes the local and systemic signs and symptoms that are being collected as adverse events. These will be solicited from the participant to ensure they are not occurring more frequently or are more severe than expected based on previous experience with the same or similar viral vectors.

With any new treatment there is always a possibility of an unexpected adverse events.

The administration of ChAdOx1-HBV in this study may interfere with the effectiveness of other vaccines subsequently administered to the participant. The ChAdOx1 vector induces anti-vector immunity in addition to an antigen-specific immune response. Of particular concern are neutralising antibodies directed against the capsid structure of the vector, which may have a negative effect on subsequent immunisations with the same or related adenoviral vector by neutralising the vector before it has a chance to transduce target cells. This effect decreases with longer interval between the vaccines [28,29]. In particular, there is a concern that the ChAdOx1-HBV administered in this study could decrease the response to the AstraZeneca COVID-19 vaccine, which has the same viral vector, especially if it is administered within 3 months of ChAdOx1-HBV. The Janssen (Johnson & Johnson) COVID-19 vaccine is also made with an adenovirus, and some interference cannot be ruled out. Therefore, it is recommended that participants in this study receive an alternative type of COVID-19 vaccine, such as an mRNA or protein vaccine, at least 2 weeks before and after ChAdOx1-HBV in this study.

There are also routinely scheduled reviews of safety and efficacy data throughout the study by the SMC. Stopping and holding rules have been defined for the study (see [Section 3.1.3](#)) and a DMC will perform a review of safety data if one of these is met.

Although this is the first time ChAdOx1-HBV has been administered to humans, the ChAdOx1 vector has been widely administered for many pathologies without significant safety concerns (see [Section 1.4](#)). Further detail is provided in the Investigator's Brochure.

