4.2 Inclusion Criteria

Participants must meet *all* the following criteria to be eligible for the study:

1. Adult males or females aged ≥ 18 to ≤ 65 years at screening
2. Body Mass Index $\leq 30 \text{ kg/m}^2$
3. Able to provide informed consent indicating they understand the purpose of, and procedures required, for the study and are willing to participate
4. If female, willing not to become pregnant up to 8 weeks after last dose of study vaccine, not breast feeding
5. If female: Not pregnant and one of the following:
 - Of non-childbearing potential (i.e. women who have had a hysterectomy or tubal ligation or are post-menopausal, as defined by no menses in ≥ 1 year)
 - Sexual abstinence, only if the participant refrains from heterosexual intercourse during the entire study period and it is the usual lifestyle of the participant
 - Of childbearing potential but agrees to practice highly effective contraception for 4 weeks prior to study vaccine and 8 weeks after study vaccine. Highly effective methods of contraception include one or more of the following:
 - Male partner who is sterile (medically effective vasectomy) prior to the female participant's entry into the study and is the sole sexual partner for the female participant
 - Combined (estrogen and progestogen containing) hormonal contraception associated with inhibition of ovulation:
 - oral
 - intravaginal

- transdermal
- Progestogen-only hormonal contraception associated with inhibition of ovulation:
 - oral
 - injectable
 - implantable
 - An intrauterine device
 - Bilateral tubal occlusion

Healthy participants (cohorts 1 and 2):

6. Considered to be healthy with no current conditions that may significantly impair participant safety or influence study results, in the opinion of the Investigator

Participants with well controlled CHB (cohorts 3 and 4):

7. Documented evidence of chronic HBV infection (e.g. HBsAg positive ≥ 6 months with detectable HBsAg levels at screening)
8. Receipt of only either entecavir or tenofovir for at least 12 months before screening
9. Virally suppressed (HBV DNA <40 IU/mL for ≥ 6 months)
10. HBsAg <10000 IU/mL

Healthy participants (cohort 5):

11. Considered to be healthy with no current conditions that may significantly impair participant safety or influence study results, in the opinion of the Investigator
12. Adult males or females aged ≥ 40 to ≤ 60 years at screening
13. Completed second dose of COVID-19 AZD1222 vaccine 10 to 18 weeks before enrolment

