Healthy participants (cohort 6):

14. Considered to be healthy with no current conditions that may significantly impair participant safety or influence study results, in the opinion of the Investigator
15. Adult males or females aged ≥ 40 to ≤ 60 years at screening
16. Received the latest dose of either Pfizer (Comirnaty®) or Moderna (Spikevax) mRNA COVID-19 vaccine 6 to 30 weeks before enrolment

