4.3 Exclusion Criteria

1. Presence of any significant acute or chronic, uncontrolled medical/psychiatric illness
2. Hepatitis C virus (HCV) antibody positive.
3. HIV antibody positive
4. History or evidence of autoimmune disease or known immunodeficiency of any cause
5. Prolonged therapy with immunomodulators (e.g. corticosteroids) or biologics (e.g. monoclonal antibodies, IFN) within 3 months of screening
6. Receipt of immunoglobulin or other blood products within 3 months prior to screening
7. Receipt of any investigational drug or vaccine within 3 months prior to screening
8. Cohorts 1-4: Receipt of any adenoviral vaccine within 3 months prior to administration of ChAdOx1-HBV on Day 0, or plan to receive an adenoviral-based vaccine within 3 months after Day 0

Cohorts 5 and 6: Receipt of any adenoviral vaccine (other than AZD1222 per inclusion criterion 13) within 3 months prior to administration of ChAdOx1-HBV on Day 0, or plan to receive an adenoviral-based vaccine within 3 months after Day 0

9. Receipt of any live vaccines within 30 days prior to screening
10. Receipt of any inactivated vaccines within 14 days prior to screening
11. History of allergic disease or reactions likely to be exacerbated by any component of the vaccine
12. Any history of anaphylaxis in reaction to vaccination
13. Malignancy within 5 years prior to screening with the exception of specific cancers that are cured by surgical resection (e.g. except basal cell skin carcinoma of the skin and cervical carcinoma). Participants under evaluation for possible malignancy are not eligible
14. Current alcohol or substance abuse judged by the Investigator to potentially interfere with participant safety and compliance
15. Significant cardiac disease or unstable uncontrolled cardiac disease
16. Any laboratory test at screening which is abnormal and which is deemed by the Investigator to be clinically significant
17. Any other finding that, in the opinion of the Investigator, deems the participant unsuitable for the study

Additionally, for healthy participants (cohorts 1, 2, 5 and 6)

18. HBsAg positive

Additionally, for participants with well controlled CHB (cohorts 3 and 4)

19. Co-infection with hepatitis delta
20. Documented cirrhosis or advanced fibrosis indicated by a liver biopsy within 6 months prior to screening.

In the absence of an appropriate liver biopsy, either 1 of the following:

- Screening Fibroscan with a result >9 kPa within ≤ 6 months of screening or

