- Amended to allow for the inclusion of participants who had received the Moderna mRNA vaccine in Cohort 6.

Amendment 8

- Amended to allow for participants to have more than two doses of a COVID-19 vaccination.

All exploratory efficacy endpoints will be analysed separately from this SAP and will be an appendix to the Clinical Study Report (CSR).

Any deviations from the protocol- specified analyses, and also deviations from analyses stated within this SAP, will be described within the CSR.

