Parameter	Cohort	Participant	Study Day	Date	Original Result	Unit	Standard Result	Unit	Toxicity Criteria	Toxicity Grade
xxxxxx	xxxxxx	xxxx	xxxx	ddmmYYYY						

Listing 16.2.8.4						
Cohort	Participant	Visit	Date/time	HIV Antibody	HCV Antibody	HDV Antibody
xxxxxx	xxxxxx	xxx	ddmmyyy hh:mm	Detected/Not Detected	Detected/Not Detected	Detected/Not Detected

Listing 16.2.8.5 Urine Pregnancy Test					
Cohort	Participant	Visit	Date	Result	Comments
xxxxxx	xxxxxx	xxxx	ddmmyyy	Positive / Negative	xxxxxxxxxxxxxxxx

Listing 16.2.9
Vital Signs

Parameter	Cohort	Participant	Visit	Date	Time Started Sitting	Collection Time	Result	Unit	Toxicity Criteria	Toxicity Grade
Temperature	xxxxxx	xxxxxx	xxxx	ddmmyyy	hh:mm	hh:mm	xx.xx	xx	xxx	x

= Baseline grade.
* = Maximum post-baseline grade.

Programming Note(s) :

List by parameter first, then subject and then day/date.
If more than one Toxicity criteria apply to a laboratory parameter (e.g. hyper and hypo) then list them all.
Include all data collected, including any unscheduled data.
If there is a tie for the maximum post-baseline result then all should be flagged.

Listing 16.2.10
Physical Examination

Cohort	Participant	Visit	Date	Body System	Finding	Comments
xxxxxx	xxxxxx	xxxx	ddmmmyyy	Skin Respiratory Cardiovascular Abdominal Lymphatic	Normal / Abnormal / Abnormal / Not Done	Not Clinically Significant / Clinically Significant / xxxxxx

A complete physical examination was performed at screening and Day 0 (prior to vaccination). Directed physical examinations were performed as required at each follow-up visits

Programming note(s):

Include complete and directed physical examinations.

Only body systems reported are included for directed physical examinations.

Listing 16.2.11
Visit Dates

Cohort	Participant	Visit	Date	Source of Unscheduled Visit	Reason for unscheduled visit	Comments
xxxxxx	xxxxxx	xxxx	ddmmyyy	xxxxxxxxxx		xxxxxxxxxxxx

Listing 16.2.12 Covid-19 Vaccination						
Cohort	Participant	Vaccination Type(1 and 2)	Date of Vaccination 1	Date of Vaccination 2	Vaccination Type (3)	Date of Vaccination 3
xxxxxx	xxxxxx	xxxx	ddmmyyy	ddmmyyy	xxxx	ddmmyyy

15.APPENDICES

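### Criterion 13 and Section 1.5.1 time cohort 5 from different COVID-19 doses, so a later mRNA dose in cohort 5 is neither restricted nor used in the analysis

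*Protocol*

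**What the plan says.** Three places in the protocol set the interval between COVID-19 vaccination and study entry.

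- Section 4.2, criterion 13 (cohort 5): "Completed second dose of COVID-19 AZD1222 vaccine 10 to 18 weeks before enrolment". Later doses are not mentioned.
- Section 1.5.1: the aim is to "keep the interval from the latest COVID-19 vaccine to a narrow window of 10-18 weeks". The next sentence gives the mRNA recipients their own interval of 6 to 30 weeks, so the 10-18 week window reads as the one for cohort 5.
- Section 4.2, criterion 16 (cohort 6): the latest dose of an "mRNA COVID-19 vaccine 6 to 30 weeks before enrolment".

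Section 3.3 recommends that participants take an alternative COVID-19 vaccine, "such as an mRNA or protein vaccine, at least 2 weeks before and after ChAdOx1-HBV in this study". This is advice, not an eligibility criterion.

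The SAP (Section 4) summarises Amendment 8 as "Amended to allow for participants to have more than two doses of a COVID-19 vaccination", without naming a cohort. Listing 16.2.12 has a separate type field for a third dose and a column headed "Date of Vaccination 3". No table, analysis set or summary uses either. SAP 10.1.3 plans no formal analysis and SAP 10.1.8 plans no subgroups.

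**The concern.** Comparing cohort 5 with cohort 6 serves a named secondary objective (SAP 5.2) and is the only comparison in the study with a sample size rationale. Its two sides are timed on different events. In cohort 6 the clock starts at the most recent mRNA dose. In cohort 5 it starts at the second AZD1222 dose, whatever came after.

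A participant with two AZD1222 doses and a later mRNA dose would carry both exposures, the second possibly more recent than the comparator permits. If a recent mRNA dose alters the ELISpot response to ChAdOx1-HBV in either direction, that effect would be read as part of the effect of prior AZD1222. As written, the analysis would not show whether this had happened.

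**Working it through.** **1. Do the two cohort 5 rules differ?** For anyone with no COVID-19 vaccine after the second AZD1222 dose, that dose is also the latest, and the rules agree. They part only for someone with a later dose. Take a second AZD1222 dose 18 weeks before entry and an mRNA dose 2 weeks before. Criterion 13 is met (18 lies in 10-18). The Section 1.5.1 window is not (2 is below 10). The Section 3.3 recommendation is met. Cohort 6 would require at least 6 weeks, so this participant is 6 − 2 = 4 weeks inside the comparator's minimum.

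**2. Does another criterion close the gap?** (Protocol Section 4.3)

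| Exclusion | Covers | Reaches a later mRNA dose? |
|---|---|---|
| 7 | investigational drugs or vaccines, 3 months before screening | not a marketed mRNA vaccine |
| 8 | "Receipt of any adenoviral vaccine (other than AZD1222 per inclusion criterion 13) within 3 months prior to administration of ChAdOx1-HBV on Day 0" | no, adenoviral only |
| 9 | live vaccines, 30 days before screening | no |
| 10 | "Receipt of any inactivated vaccines within 14 days prior to screening" | no, inactivated only |

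Such a participant fails no listed criterion. Failing eligibility is one of the two grounds that SAP 9.2 names for leaving the per-protocol set, so neither named ground removes them from the immunogenicity set.

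**3. The plan's own figure.** Protocol 10.1 and SAP 8 give a mean of 1,000 ± 500 SFU from three adults, 15 per cohort and a 45% decrease (450 SFU). Alpha, sidedness and power are not stated. Reading 500 as the SD:

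- SE = 500 × √(1/15 + 1/15) = 182.6 SFU.
- One-sided 5%: power = Φ(450/182.6 − 1.645) = 79.4%. The decrease detectable with 80% power is (1.645 + 0.842) × 182.6/1,000 = 45.4%. This reproduces the figure.
- Two-sided 5%: power = Φ(450/182.6 − 1.960) = 69.3%. This does not.

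The one-sided version is used below only as a yardstick, since the SAP plans no test.

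**4. How far could a booster move the comparison?** The documents supply neither input, so both are assumptions. Let p be the share of cohort 5 boosted and b the proportional change in their response. With no true AZD1222 effect, the apparent decrease is −1,000 × p × b SFU, and the chance that a one-sided 5% test would call it real is Φ(decrease/182.6 − 1.645).

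| p | b | Apparent decrease (SFU) | False-positive rate |
|---|---|---|---|
| 0, or any | any, or 0 | 0 | 5.0% |
| 0.2 (3 of 15) | −30% | 60 | 9.4% |
| 0.2 | +30% | −60 | 2.4% |
| 0.5 | −30% | 150 | 20.5% |
| 0.5 | +30% | −150 | 0.7% |

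The first row is the protocol's own expectation for mRNA vaccines.

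**5. Precision of a summary without boosted participants.** With k of 15 set aside, SE = 500 × √(1/15 + 1/(15 − k)). For assumed k = 3, 5 or 8, one-sided power for a 45% decrease is 75.1%, 71.2% or 62.6%, and the decrease detectable with 80% power is 48.2%, 50.8% or 56.9%.

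**The case against.** The protocol consistently describes cohort 5 as having two AZD1222 doses and cohort 6 as having at least two mRNA doses. Appendix 2 shows that, among the criteria, Amendment 8 changed only criterion 16. The secondary objective itself counts 10-18 weeks from AZD1222, which fits criterion 13. The SAP's one-line summary of Amendment 8 and a listing with a third-dose column therefore do not show that boosted cohort 5 participants were expected. That stands, but two doses of AZD1222 is nowhere stated to mean no other COVID-19 vaccine.

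A reader might infer that boosters within days of Day 0 were intended or likely. The criteria do not prevent it, but Sections 1.5.1 and 3.3 both point the other way. A reader might also infer that the comparison has lost its ability to isolate AZD1222. It never had it: allocation is non-randomised and the windows differ by design (10-18 against 6-30 weeks).

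Some protection exists already. Vaccines in the previous 28 days are recorded with prior medications (Protocol 5.9). Reactogenicity is assessed before vaccination on Day 0, so symptoms already present would be visible, and a claim that booster reactions would simply be credited to ChAdOx1-HBV goes too far. ELISpot results are HBV-peptide specific, background-subtracted and also shown as change from baseline, although this would not remove an effect on priming. The data review meeting can exclude specific data, but no rule for a third dose is set in advance.

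**Conclusion.** The inconsistency is in the current text: criterion 13 and Section 1.5.1 anchor the cohort 5 window on different doses, criterion 16 anchors cohort 6 on the latest, and no exclusion covers a later mRNA dose. The consequence is possible added confounding in a non-randomised, descriptive comparison.

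Its size cannot be given. It depends on how many cohort 5 participants had a later dose and on whether that dose changes the HBV T cell response. Neither is documented, and the protocol expects no mRNA interference, so the bias may be zero. The figures in step 4 of the working show sensitivity to assumed inputs and are not estimates. The point does not affect the stated sample size or its 45% figure. It is worth correcting because the remedy is cheap and the third-dose data are already to be listed.

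**What to change.** 1. **Protocol.** Reconcile criterion 13 with Section 1.5.1 so that both time the same event. Which event is for the sponsor to decide. A ban on any further COVID-19 vaccine would go beyond what Section 1.5.1 says and is not needed to remove the contradiction.
2. **SAP.** Use the third-dose type and date in Listing 16.2.12 to flag cohort 5 participants who had a COVID-19 vaccine after their second AZD1222 dose. Repeat the cohort 5 columns of Table 14.2.4 without them as a descriptive sensitivity summary, and keep the full table. If nobody is flagged, a footnote saying so closes the matter.

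The cost is one flag, one extra set of columns on a smaller n, and possibly a slightly smaller recruitment pool for cohort 5, depending on how the passages are reconciled. The SAP step needs no new data and is useful even if enrolment has finished.

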4 STUDY POPULATION

4.1 Number of Participants

It is planned that 40 healthy participants and 12 participants with CHB infection and virally suppressed with oral antiviral medication will be enrolled in the study. Chronic HBV participants will be recruited/deemed eligible by hepatologists, infectious disease specialists or physicians experienced in treating CHB participants. Centres not meeting the enrolment expectations will be considered for replacement with or addition of a new site. If participants leave the study before all follow-up visits are completed (for any reason), then these may be replaced at the discretion of the study team. A log of all participants enrolled into the study (i.e. having given informed consent) will be maintained in the Investigator's Site File (ISF) at the study centre irrespective of whether they have treated with vaccine or not.

A total of 10 healthy participants and 12 participants with CHB infection is considered sufficient to confirm the safety, tolerability and immunogenicity of ChAdOx1-HBV and to answer the objectives of the study before progressing to larger studies. An additional 30 healthy participants (15 who have received two doses of AZD1222 and 15 who have received at least two doses of either Pfizer or Moderna mRNA COVID-19 vaccine) will be recruited to assess whether prior receipt of AZD1222 results in decreased T cell responses to ChAdOx1-HBV.

The statistical considerations used to determine the number of participants planned and evaluable are presented in [Section 10.1](#).

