10. PLANNED STATISTICAL METHODS

10.1. Statistical Considerations

10.1.1. General definitions

Definition of baseline

Baseline is defined as the last non-missing value for a participant, for the particular parameter, that is prior to the administration of study vaccine.

Study completion definition

A participant completes the study by engaging in study activities up to and including the End of Study Visit at Day 168 (+/- 7 days), for cohorts 1 to 4, and Day 84 (+/- 7 days) for cohorts 5 and 6.

Treatment Group

There are six treatment groups in this study; the Healthy Participants and CHB participants are split into high and low doses of vaccination. Healthy participants in the high dose group are further split into those with no previous exposure to ChAdOx1 vectored vaccines, those with recent previous exposure to Covid-19 ChAdOx1 vectored vaccine (cohort 5) and those with previous exposure to Covid-19 mRNA based vaccines (cohort 6).

Results below limit of detection and quantification

Immunogenicity results that are below the limit of quantification or detection (i.e. reported as <X or BLQ) will be replaced by 0 for any summaries but will be listed as reported.

Geometric Mean and Standard Deviation

The geometric mean (GM) and geometric standard deviation (GSD) are obtained by calculating the mean and SD of the log-transformed data and back-transforming these. If there are any zero values in the data a small number should be added to all values before log-transformation and then subtracted from the resulting GM. This small number will be 1 unless stated otherwise.

GM = antilog (mean (log(value + S))) – S, where S is a small number, relative to the non-zero results.

GSD = antilog(standard deviation(log(value + S)))

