Categorical variables will be summarised using proportions (counts and percentages). All percentages in summary tables will be calculated using as the denominator, either the participant analysis set or the number of non-missing observations. The specific approach is detailed within each (relevant) table template (Section 14).

All collected data will be included within participant listings.

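### Cohort 6's written entry rules do not carry its two-mRNA-dose definition or bar earlier AZD1222, and the cohort 5 window is counted to a different date from the one in the objective

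*Protocol*

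**What the plan says.** **Cohort 6 as described.** Protocol 4.1 plans for "15 who have received at least two doses of either Pfizer or Moderna mRNA COVID-19 vaccine". The synopsis, Protocol 3.1.2 and SAP 6 say the same.

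**Cohort 6 as admitted.** Criterion 16 in Protocol 4.2 reads: "Received the latest dose of either Pfizer (Comirnaty®) or Moderna (Spikevax) mRNA COVID-19 vaccine 6 to 30 weeks before enrolment". It sets no minimum number of doses and is silent on other COVID-19 vaccines. SAP 4 gives the purpose of the last amendment: "Amended to allow for participants to have more than two doses of a COVID-19 vaccination".

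**Adenoviral exclusion.** For cohorts 5 and 6, exclusion 8 in Protocol 4.3 removes: "Receipt of any adenoviral vaccine (other than AZD1222 per inclusion criterion 13) within 3 months prior to administration of ChAdOx1-HBV on Day 0". (Criterion numbers here follow Protocol 4.2 and 4.3; the synopsis numbers the exclusions differently.)

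**Cohort 5 window.** Criterion 13 requires the second AZD1222 dose 10 to 18 weeks before enrolment. The secondary objective (synopsis and SAP 5.2) counts the same 10 to 18 weeks back from ChAdOx1-HBV.

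**Analysis.** SAP 10.1.1 describes cohort 6 by its previous mRNA exposure and does not require absence of ChAdOx1 exposure. SAP 9.2 removes participants for a wrong vaccine or dose or for major deviations, with an open-ended list settled at the data review meeting. SAP 10.1.3 plans no formal test.

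**The concern.** The cohort 5 v 6 contrast is the only comparison that addresses the interference objective, and it needs a comparator without prior exposure to the vector. Protocol 4.2 makes the listed criteria decisive for eligibility and Protocol 9.1 allows no deviation from them, so a definition that stands only in the descriptive sections does not control entry.

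If prior AZD1222 does suppress the response, an exposed control lowers the cohort 6 mean and shrinks the apparent decrease. A cohort 5 participant dosed after week 18 could act in the same direction, because Protocol 3.3 says the vector effect weakens as the interval lengthens. Such a participant would also lie outside the interval the objective names. Both errors favour a finding of no interference.

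**Working it through.** **1. Eligibility logic.** Take 3 months as about 13 weeks and suppose, for simplicity, that enrolment falls on Day 0. Each case is a healthy person aged 40 to 60 whose latest mRNA dose was 6 to 30 weeks earlier.

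| History before Day 0 | Criterion 16 | Exclusion 8 | Two-mRNA-dose definition |
|---|---|---|---|
| Two AZD1222 (second at 14 weeks), one mRNA at 7 weeks | met | not triggered | not met |
| AZD1222 more than 3 months ago, then two mRNA | met | not triggered | met |

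The first person also meets criterion 13, so the two cohorts' rules are not mutually exclusive. Restoring the two-dose minimum would remove the first case but not the second, so both repairs are needed. The AZD1222 exception in exclusion 8 is worded for cohorts 5 and 6 together. Whether AZD1222 at 10 to 13 weeks is barred from cohort 6 is therefore also open to argument.

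**2. What the SAP could detect.** SAP 10.1.2 states: "All collected data will be included within participant listings". Listing 16.2.12 gives three dose dates and a separate type for dose 3, but one shared type field for doses 1 and 2. A mixed first course shows only if two products are entered in that field. SAP 10.7.2 names the anti-vector neutralising titre as a measure, yet the shell of Listing 16.2.6.5 shows sample collection only, with no result column.

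**3. Interval at dosing.** Protocol 4.1 equates being enrolled with having given consent. Protocol 13.4 speaks of people who consent but are not subsequently enrolled, and SAP 9.1 refers to a dose assigned at enrolment; both imply a later step. Screening may start at Day -42.
- Enrolment on Day 0: at most 18 weeks from AZD1222 to dosing.
- Enrolment at consent: up to 18 + 42/7 = 24 weeks. For criterion 16, up to 30 + 6 = 36 weeks.

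**4. The plan's own sample size.** Protocol 10.1 and SAP 8 give mean 1,000, +/-500 (taken here as the SD), 15 per cohort and a 45% decrease (450 units), without alpha, sidedness or power. By the normal approximation, z = 450 / (500 × √(2/15)) = 2.465. Power is 69.3% two-sided at 5% and 79.4% one-sided (66.3% and 77.6% with the t distribution). Fifteen per cohort is therefore close to a one-sided 5%, 80% design, which needs 16; the two-sided version needs 20.

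**5. Illustration of dilution.** Let k of 15 controls be ChAdOx1-exposed and carry a share f of the 450-unit suppression. Both are assumptions.

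Cohort 6 mean = 1,000 − 450 × f × k/15; apparent decrease = 1 − 550/mean.

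| k | f | Cohort 6 mean | Apparent decrease | Two-sided 5% power (simulated t-test, SD 500) |
|---|---|---|---|---|
| 0 | – | 1,000 | 45.0% | 66% |
| 1 | 0.5 | 985 | 44.2% | 63% |
| 1 | 1 | 970 | 43.3% | 59% |
| 3 | 0.5 | 955 | 42.4% | 57% |
| 3 | 1 | 910 | 39.6% | 45% |

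The power column depends on the constant SD. If the SD scales with the mean (CV 50%, also an assumption), the standard error is √((500² + 275²)/15) = 147.3. Normal-approximation power with no exposed control is then 86.3% rather than 69.3%.

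**The case against.** **Intent is clear.** The two-dose minimum is stated in several places, and the last amendment was meant to admit more doses, not fewer. The omission is most likely a drafting slip, and a one-dose participant contradicts the cohort description. That is fair, but AZD1222 followed by two mRNA doses contradicts no text at all.

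**Safeguards exist.** Exclusion 17 lets the investigator reject anyone thought unsuitable, eligibility is re-checked on Day 0, Day 0 neutralising antibodies are sampled in cohorts 5 and 6, and the data review meeting may exclude participants. These could catch a case, but none is a stated rule, and someone who breaks no criterion gives SAP 9.2 no explicit ground for removal.

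**Interference may be absent.** Protocol 1.5.1 reports no effect of an earlier ChAdOx1 vaccine on the AZD1222 response, and says the interval effect has not been clearly tied to anti-vector antibodies. The bias is therefore conditional on interference existing.

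**The effect may be small.** One exposed control moves the estimate little. A reader might add that AZD1222 admitted under these rules must be old and so only weakly suppressive. The documents do not support that: AZD1222 at about 13 to 18 weeks passes exclusion 8 and matches cohort 5's exposure. No document supplies a suppression fraction either way.

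**Enrolment.** A reader might infer that the term is undefined. It is not, since Protocol 4.1 glosses it as consent. The supportable point is inconsistent use and a mismatch of anchor with the objective. The 24-week figure is a worst case, needing consent at week 18 and the full screening period.

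**Conclusion.** The point holds on the current text and should be fixed. Criterion 16 does not carry the definition of cohort 6, no explicit criterion bars AZD1222 given more than 3 months before Day 0, and criterion 13 and the objective count to different dates.

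The direction of any bias is towards no interference, provided interference exists. Its size is unknown. The dilution figures rest on assumed values of k and f, and the power figures also on a constant SD; power is of limited relevance because no test is planned. The 24-week interval rests on reading enrolment as consent.

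A reader might go further and conclude that the comparator was contaminated or that the comparison is invalid. The documents show only that the rules permit such participants, not that any were enrolled.

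**What to change.** **Protocol.** Reconcile criterion 16 with section 4.1, and state that cohort 6 must have had no AZD1222 or other ChAdOx1-vectored vaccine. Count the windows in criteria 13 and 16 to Day 0, as exclusion 8 already does, so that they match the objective.

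**SAP, before database lock** (useful even if recruitment is complete):
- Show product and date for each COVID-19 dose in Listing 16.2.12.
- Report the Day 0 anti-ChAdOx1 titre, for example as a result column in Listing 16.2.6.5.
- State in advance that cohort 6 participants with prior ChAdOx1 exposure are left out of the cohort 5 v 6 comparison, report how many, and show the all-participants summary beside it.
- Summarise weeks from the last AZD1222 dose to Day 0, and base the 10-to-18-week conclusion on participants inside that window at Day 0.

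**Cost.** A few eligibility sentences, two listing changes, one analysis rule and one summary. Sites may need to answer vaccine-history queries, and a few participants may be lost from the comparison.
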